## STUDY SUMMARY

Study Title:	Cardiovascular risk factors and multimorbidity after renal transplant
Local Study Reference:	UHDB/2025/044
Study Design:	Prospective cohort study
Study Participants:	Patients after renal transplants, who are adults (age $\geq 18$ )
Planner Number of Sites:	1 site
Planned Sample Size:	30 patients
Treatment Duration:	Not applicable
Follow Up Duration:	1 year
Planned Start Date:	01/08/2025
Planned Recruitment End Date:	Patient recruitment will begin once all necessary approvals are in place, with an anticipated recruitment period of 12 months, to finish 01/08/2026
Planned Study End Date:	The study will end when the last patient completes their study visit. Total duration of the study will be 24 months, to finish 01/08/2027
Research Question/ Aims:	To better understand patterns of development of cardiovascular risk factors and multimorbidity in the year after renal transplant

**FUNDING AND SUPPORT IN KIND**

Funder(s)	Financial and Non-Financial Support Given
N/A	

## **ROLES & RESPONSIBILITIES**

### **Sponsor**

The Sponsor, University Hospitals of Derby & Burton NHS Foundation Trust, take on overall responsibility for appropriate arrangements being in place to set up, run and report the research project.

### **Study Management Committees**

The Centre for Kidney Research and Innovation (CKRI) at the University of Nottingham will be overseeing the study.

### **Protocol Contributors**

The Chief Investigator and co-investigators have been involved in the development of this protocol. Protocol contributors are responsible for inputting into the design of the study, ensuring that it is designed rigorously, transparently and efficiently.

## LIST OF ABBREVIATIONS

AE	Adverse Event
CI	Chief Investigator
CRF	Case Report Form
DMEC	Data Monitoring and Ethics Committee
GCP	Good Clinical Practice
GMP	Good Manufacturing Practice
ICF	Informed Consent Form
ICH	International Conference on Harmonisation of technical requirements for registration of pharmaceuticals for human use.
ISF	Investigator Site File
ISRCTN	International Standard Randomised Controlled Trials
NHS R&D	National Health Service Research & Development
PI	Principal Investigator
PIC	Participant Identification Centre
PIS	Participant Information Sheet
QA	Quality Assurance
QC	Quality Control
RCT	Randomised Control Trial
REC	Research Ethics Committee
SAE	Serious Adverse Event
SDV	Source Data Verification
SOP	Standard Operating Procedure
TMG	Trial Management Group
TSC	Trial Steering Committee
TMF	Trial Master File

## STUDY FLOW CHART

## STUDY PROTOCOL

### 1. BACKGROUND

At the end of 2022 39,874 adult patients in the UK were living with a kidney transplant, representing 56.2% of the population on kidney replacement therapy. Kidney transplant remains the gold standard of renal replacement therapy and confers benefits in survival and quality of life over dialysis. Short term survival post-transplant is good, with 94% adjusted 5 year survival in the UK for a transplant from a living donor and 87% for a deceased donor from the most recent UK renal registry data.

A high proportion of renal transplant patients have a high burden of comorbidities. Increasing multimorbidity has been shown in the general population to increase risk of premature death and hospital admissions and is associated with poorer function and greater economic costs. Much of the data in kidney transplant recipients focusses on comorbidity burden at time of transplant and the predictive use of this data for outcomes. There is little available data on the patterns and progression of multimorbidity for patients living with renal transplant. An assessment of the wider CKD cohort was undertaken using medical records and self reporting to understand multimorbidity, with a group of 176 transplant patients in the UK and showed that 92% had at least one comorbidity in addition to CKD. The most common comorbidity was hypertension (60.1%), followed by musculoskeletal conditions (40.9%) and then cardiovascular disease and diabetes. However, there is no data available, in this study or others, on the longitudinal development of comorbidities after transplant receipt. There is also no data available on the impact of multimorbidity on the quality of life of kidney transplant recipients. Although there is evidence for development of specific conditions, this has not been examined within the context of multiple long term health conditions.

There is no consensus on the measurement of multimorbidity, and no consensus on which comorbid conditions should be used in a count. Expert reviewers suggest the conditions used to define multimorbidity should be guided by health impact and may be tailored to a study population. No such work has taken place in the kidney transplant population.

A major comorbidity at time of transplantation and in post transplantation is cardiovascular disease and this is a major cause of death for patients with a renal transplant. Although the risk of adverse cardiovascular outcomes is decreased compared to patients on dialysis it is significantly increased compared to the general population. In addition, there is a high prevalence of both hypertension and diabetes within the transplant population. As well as these being common comorbidities to have at time transplant, patients commonly develop post-transplant diabetes. Alongside these factors, the risk of cardiovascular disease is also increased by raised BMI and lipid levels, which are commonly raised in renal transplant patients. The interaction between these risk factors and transplant specific factors such as immunosuppressive medication and post-transplant weight gain contribute to significant cardiovascular risk. There is no consensus on specific post-transplant treatment targets or interventions. Much of the evidence available for the timeline of development of cardiovascular risk factors is limited to retrospective cohort data and does not place cardiovascular disease within the context of multimorbidity. In addition, much of the data predates current immunosuppression strategies and cardiovascular management strategies.

Obesity is a significant factor in development of multimorbidity in the wider population. In particular it is associated with development of cardiovascular risk factors and cardiovascular disease in the wider

chronic kidney disease population as well as the transplant population. In the general population obesity contributes to frailty, and poor health-related quality of life, and can lead to worsening multimorbidity. There is also significant sarcopenia within the CKD and transplant population. Weight gain over the first year post transplant has been well recognised. However, assessing this using only body mass index (BMI) has limitations in the CKD and transplant populations as it does not take into account the possible normalisation of a pre-existing malnourished state. Using body composition techniques such as bio-impedance has shown changes in body composition post renal transplant, which has been related to muscle strength and fat distribution although this has not been correlated with function, multimorbidity, or development of cardiovascular risk factors..

## **2. RATIONALE**

In this exploratory study we aim to understand what happens to multimorbidity over the first year following transplant, including modifiable cardiovascular risk factors. We would then plan to plan and undertake a larger prospective longitudinal study over a longer period of time based on these findings.

We aim to explore the development of multimorbidity on patients after kidney transplantation-the patterns of multimorbidity across conditions, common comorbidities, and progression of multimorbidity. We plan to use a functional measure to understand how this might relate patient's experience.

We aim to measure the baseline characteristics of cardiovascular risk factors in the patient population as they return from transplant surgery to their referring centre, and then how these develop in the first year. The results of the study would aim to contribute to an evidence base regarding cardiovascular risk factors and identify targets for intervention within the first year. Early identification of modifiable risk factors can contribute to improvement of cardiovascular outcomes and graft survival.

We plan to use bioelectrical impedance to assess body composition and further understand the nature of weight gain post-transplant and how this relates to function, multimorbidity, exercise and other cardiovascular risk factors.

We also plan to recruit some patients into a qualitative study to help us understand possible barriers to improving modifiable cardiovascular risk factors with the aim of improving the effectiveness of any targeted interventions.

### **3. OBJECTIVES AND OUTCOME MEASURES/ ENDPOINTS**

#### **3.1. Objectives**

##### **Primary aims:**

- To assess the changes over time of multimorbidity in the one year post kidney transplantation.

##### **Secondary aims:**

- To assess the changes over time of cardiac risk factors in the one year post kidney transplantation.
- Understand the barriers to improved cardiovascular health and impact of multimorbidity using structured interviews.
- Understand body composition changes over the one-year post transplant and how this relates to functional status.

#### **3.2. Outcome**

##### **Primary outcomes:**

1. To measure the number and type of comorbidities of patients in the one year post renal transplantation.
2. To measure the cardiovascular risk factors over one year post transplant. (Blood pressure, lipid levels, BMI, HbA1c.).

##### **Secondary outcomes:**

1. Use bioimpedance to estimate body composition changes over the year post transplantation
2. Use functional measures to assess impact on patient of multimorbidity, body composition and time out from transplantation.
3. Use qualitative methods in a structured interview format to understand barriers to improved cardiovascular health and impact of multimorbidity.

### **4. STUDY DESIGN**

#### **Study Part 1**

The study is a prospective cohort study. Patients returning for follow up at the study centre post hospital discharge will be screened for eligibility. Demographic information will be recorded at baseline. This includes primary renal diagnosis, if participant had been on dialysis, type of dialysis and dialysis vintage. At each study visit the following data will be collected: eGFR (using the creatinine-based formula (CKD-EPI)), HbA1c, lipid levels, urine ACR, clinic blood pressure, weight, height, smoking status, functional status using the KDQOL 36 and sit to stand, comorbidities, medications. This will be done at the baseline visit, three months, 6 months and one year after initial study visit.

## **Study Part 2**

For those participating in the body composition element of the study this will take place at the baseline study visit, and at 6 months and one year after initial study visit. Patients must enter part 2 of the study at the first study visit. Patients must be entered into part 1 of the study to enter into part 2. All patients who enter the study will be offered part 2 of the study unless they are ineligible.

## **Study Part 3**

At the one-year study visit we will recruit for the structured interview element of the study. This will take place as soon as can be arranged after this visit. The interviews will be carried out face to face. We aim to recruit 10 participants for the interview. They will be recorded using trust recording equipment and transcribed and analysed by the research team. We will use content analysis to understand the themes of barriers to healthy lifestyle and perceptions of health after renal transplantation. We will screen and consent all participants until 10 are recruited for this element of the study.

## **5. STUDY SETTING**

Study visits will be at the Royal Derby Hospital in the renal outpatient unit where participants attend for their usual renal outpatient appointments. Patients will be recruited from transplant coordinator data as they return from transplant.

## **6. ELIGIBILITY CRITERIA**

### **6.1. Inclusion Criteria**

- Age  $\geq$  18 years old
- Capable of giving informed consent
- In receipt of a single organ renal transplant and being followed up by UHDB as the referring team.

### **6.2. Exclusion Criteria**

#### **Exclusion criteria for main study**

- Graft failure before return to follow up

#### **Exclusion criteria for body composition**

- Pregnancy
- Subjects with known neuromuscular diseases, e.g. myopathy, muscular dystrophy, muscular atrophy
- Patients with pacemakers

## **7. STUDY PROCEDURES**

### **7.1. Recruitment**

#### **7.1.1. Patient Identification**

Patients will be identified by the transplant coordinator on return to UHDB after transplant. All patients receiving a transplant will be screened and assessed by the eligibility criteria.

#### **7.1.2. Screening**

Once identified, the investigators will ask the potential participants if they were interested in the study, and a PIS will be provided at the time. Patients will be contacted either at a face-to-face clinic visit or via phone call for recruitment. The participants will be given time to read the PIS and at agreed time, recontacted to discuss any queries and check if they would like to consent for participation.

## **7.2. Consent**

Informed consent must be obtained prior to the participant undergoing procedures that are specifically for the purposes of the study (including the collection of identifiable participant data, unless the study has prior approval from the Confidentiality Advisory Group (CAG) and the REC).

Once potential participants have had sufficient time to consider the PIS and opportunity to discuss any questions, the investigator will take informed, written consent. Participants may withdraw consent at any point and will be withdrawn from the study.

Translation services via the clinical setting (language line) will be available for those whom English is not their first language for all aspects of the study. Translation services for information sheets and consent forms will be available in other languages and also for study visits, phone calls and structured interviews if required.

The Principal Investigator (PI) retains overall responsibility for the informed consent of participants at their site and must ensure that any person delegated responsibility to participate in the informed consent process is duly authorised, trained and competent according to the REC approved protocol and applicable guidelines and regulations.

## **7.3. Study Assessments**

Data will be collected from medical records, confirmed with participants and entered into the CRF: Participants will have demographic information recorded at baseline. This will include age, primary renal diagnosis, dialysis modality and vintage, and transplant details including deceased or living donor, induction regime, and length of hospital stay for transplant operation.

At each study visit collect the following data: eGFR (using the creatinine-based formula (CKD-EPI)), HbA1c, lipid levels, urine ACR, standardised office blood pressure, weight, height, smoking status, functional status, comorbidities, medications.

Functional status will be assessed using the KDQOL SF 36 and a sit-to-stand test. This is a validated survey assessing quality of life for patients with kidney disease. KDQOL has been translated and validated in a number of languages and if these are available will be used when applicable, along-side translation services in place in the renal department when needed.

For those in group 2 bioimpedance will be done at baseline, 6 months, and one year. Bioimpedance will involve the Inbody bioimpedance machine in the UHDB renal outpatients department. These involves participants wearing light clothing and takes approximately 5 minutes. This measures body composition, which divides weight into different components.

The structured interview will take approximately 20 minutes, and will take place at the closest available outpatient clinic appointment to the one year follow up visit. This will be recorded via already available transcription devices and transcribed by the study team.

Study visits will be aligned to the closest clinic appointment. Study visits will be at the first available opportunity after return to follow up at UHDB, then subsequently at one month, three months, six months and one year after this visit. Blood tests will be taken as part of usual standard of care and data collected from these results resulting in no extra blood tests for the patient.

There will be no compensation for participants. We will offer refreshments for the study assessments from within the department. If a patient requires transport this will be part of their normal clinic arrangements. We discussed the format of the assessments with our local PPIE group who felt that the arrangements were satisfactory.

#### **7.4. Withdrawal Criteria**

Participants will be withdrawn from the study if they withdraw consent to participate at any time. Participants do not have to provide a reason for withdrawal of consent. Subjects will also be withdrawn if it is deemed unsafe or is found to be impossible to proceed in the opinion of the investigators.

The participants will be made aware that this will not affect their future care. Participants will be made aware (via the information sheet and consent form) that should they withdraw the data collected to date cannot be erased and may still be used in the final analysis.

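### Section 7.4 does not confine investigator-led withdrawal to the affected procedure or provide for record-based follow-up, so primary data that routine care still generates may be lost

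*Protocol*

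**What the plan says.** Section 7.4 gives two routes out of the study. The first is the participant's own decision: "Participants will be withdrawn from the study if they withdraw consent to participate at any time". The second, in the same paragraph, is the investigators': "Subjects will also be withdrawn if it is deemed unsafe or is found to be impossible to proceed in the opinion of the investigators". The second route is mandatory in form, rests on judgement, and defines neither ground. Because it follows directly on withdrawal from the study, the natural reading is that it operates at the same level.

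On data, Section 7.4 says that participants will be told that "should they withdraw the data collected to date cannot be erased and may still be used in the final analysis". Nothing is said about data that arise later in the medical record.

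The primary aim (Section 3.1) is "To assess the changes over time of multimorbidity in the one year post kidney transplantation". The first primary outcome (Section 3.2) is "To measure the number and type of comorbidities of patients in the one year post renal transplantation"; the second covers blood pressure, lipids, BMI and HbA1c. Section 7.3 describes the sources: "Data will be collected from medical records, confirmed with participants and entered into the CRF", and "Blood tests will be taken as part of usual standard of care and data collected from these results". Visits are fitted to the nearest clinic appointment, and Section 12.1 rates risk as low because there is no treatment.

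**The concern.** In a study without an intervention, what could become unsafe or impossible is mainly a study-specific task (sit-to-stand, KDQOL, bioimpedance, interview) or attendance itself. None of those tasks produces a primary outcome. Attendance does contribute, because it allows confirmation with the participant and standardised measurement, but most of the underlying primary information goes on being generated in usual care.

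Serious new illness is a plausible reason for an investigator to decide that someone cannot continue. New illness is also what the primary aim sets out to measure, so withdrawal could depend on the outcome. The analysis cannot repair this afterwards. A longitudinal model uses the visits before withdrawal but cannot see a condition that arises at or after it. If that condition caused the withdrawal, a missing-at-random assumption is doubtful. Section 10.4 excludes imputation, and a statistical analysis plan cannot recover data that were never collected.

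**Working it through.** The protocol states no withdrawal rate, effect size or power calculation, so there is no figure to reproduce. The check has two parts.

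**1. Reading the sections together**

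- *Entry.* Section 6.2 excludes people with pacemakers, pregnancy or known neuromuscular disease from body composition only; they can still enter Part 1. Section 12.1 repeats this for pacemakers.
- *Follow-up.* Section 7.4 has no matching part-level rule. A participant who receives a pacemaker during the year meets the safety exclusion for bioimpedance only, but Section 7.4 does not say that only bioimpedance stops. The event bears on the comorbidity outcome, so it matters that the participant's follow-up continues.
- *Sources.* Sections 7.3 and 7.5 take bloods from routine care, and Section 7.3 takes data from medical records. Blood pressure, weight, height and comorbidities are also listed as study-visit items, so the primary data are not purely a record extract.
- *Analysis.* Section 10.3.1 reports losses and reasons, Section 10.3.2 plans longitudinal modelling of unspecified type, and Section 10.4 rules out imputation. These disclose a gap or work around it; none fills it.

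**2. Scale, on assumed values**

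From the protocol: N = 25 (Section 10.2) and N = 30 (Study Summary). The two disagree, so both are used. Assumed: k participants withdrawn; e participants who truly gain a condition, with all k among them and their new conditions unrecorded; and only those remaining counted at one year.

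Observed share = (e − k) / (N − k).

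| k | N = 25, true 40% (e = 10) | N = 30, true 40% (e = 12) | N = 25, true 20% (e = 5) | N = 30, true 20% (e = 6) |
|---|---|---|---|---|
| 1 | 9/24 = 37.5% | 11/29 = 37.9% | 4/24 = 16.7% | 5/29 = 17.2% |
| 2 | 8/23 = 34.8% | 10/28 = 35.7% | 3/23 = 13.0% | 4/28 = 14.3% |
| 3 | 7/22 = 31.8% | 9/27 = 33.3% | 2/22 = 9.1% | 3/27 = 11.1% |

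For the mean number of conditions gained, the understatement among those remaining is (k/N) × gap, where gap is the mean gain of the withdrawn minus that of the others. With k from 1 to 5 and gap from 0.5 to 2 conditions:

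- N = 25: from 1/25 × 0.5 = 0.02 to 5/25 × 2 = 0.40 conditions.
- N = 30: from 1/30 × 0.5 = 0.017 to 5/30 × 2 = 0.33 conditions.

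Each withdrawal is 1/25 = 4.0% or 1/30 = 3.3% of the cohort. The effect can be negligible or material, and no figure in the protocol decides which.

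**The case against.** A reader might infer that the sickest participants will leave the primary outcome as their multimorbidity worsens. The documents do not support that. Section 7.4 does not tie withdrawal to new disease, and failing one assessment does not automatically trigger it. Where the main activity is reading records and clinic results, an investigator may seldom find continuation unsafe. The design is already modular, and Section 10.4 expects some items to be absent, so a participant with a missed test can stay in.

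A reader might also infer that only data from before withdrawal may be used. Section 7.4 does not say so. It says that existing data are kept; on later record data it is silent and contains no prohibition. Nor does Section 7.2 help a bias argument: "Participants may withdraw consent at any point and will be withdrawn from the study" concerns consent, not an investigator's judgement about health.

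On size, the illustration sits at the upper end. Earlier visits are kept and modelled, and reported reasons for loss would often document the event. Records-only values are also not equivalent to visit values: they are unconfirmed, and blood pressure may not be standardised. The participant information sheet and consent form are not available here and may already offer partial withdrawal.

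All of this stands, and it limits the strength and size of the point. It does not remove the gap: the rule is mandatory, its scope is unstated, and nothing provides for collecting later record data.

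**Conclusion.** The point holds as a weakness in how withdrawal is specified, not as a demonstrated bias. Section 7.4 neither limits investigator-led withdrawal to the affected procedure or part nor provides for continued collection from routine records. Loss of late conditions and risk-factor values is therefore possible, and the likely direction is to understate the one-year change in multimorbidity.

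The size is unknown. The three-withdrawal figures rest on assumed event shares, on every withdrawn participant having gained a condition, and on that condition going unrecorded. With one withdrawal the same arithmetic moves a true 40% by only about 2 percentage points. For a small exploratory cohort this is a cheap improvement worth making before or early in recruitment, and not a flaw that undermines the study.

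**What to change.** Amend Section 7.4 as follows:

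- (a) If a study procedure is unsafe or impossible, only that procedure or part stops, the reason is recorded, and the participant stays in Part 1.
- (b) If visits cannot continue, comorbidities, routine bloods, clinic blood pressure, weight and medications are taken from the UHDB record at the scheduled time points. These values are flagged as records-only: not confirmed with the participant, and blood pressure possibly not standardised.
- (c) Collection ends when the participant withdraws consent, with a records-only option offered at that point.

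Align Section 7.2, and align the participant information sheet and consent form if they do not already say this. It would also help to report withdrawals by reason with last known comorbidity status.

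The cost is one wording amendment and a brief record review per affected participant, with no added visits or tests. The change concerns data collection only and alters no clinical care. It would not recover values for participants who die or move away.
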